For secondary endpoints, all binary endpoints will be analyzed in the same way as the primary endpoint for the overall study. For continuous endpoints, a mixed-effect model with repeated measures (MMRM) will be used. This model will include the factors (fixed effects) for treatment group, visit, treatment-by-visit interaction, and relevant baseline value when modeling the change from baseline. Within the framework of MMRM, the treatment difference will be tested at each time point.

All secondary endpoints will be evaluated at the 5% level of significance, without adjustments for multiple comparisons.

The pharmacokinetic (PK) concentration population is defined as all enrolled subjects who received at least 1 dose of PF-06651600 and in whom at least 1 concentration value is reported.

The safety data will be summarized in accordance with Pfizer Data Standards. All subjects who receive investigational product (safety population) will be included in the safety analyses. All safety data will be summarized descriptively.

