### **9.2.3. Analysis of Secondary Endpoints**

For all regions, analyses of secondary endpoints that are not  $\alpha$  controlled will use the approach outlined below.

Secondary endpoints that are binary variables will be analyzed using the same approach as Analysis 1 in [Table 6](#).

For continuous endpoints, a mixed-effects model with repeated measures (MMRM) will be used. This model will include the factors (fixed effects) for treatment group, visit, treatment-by-visit interaction, and relevant baseline value when modeling change from baseline. Within the framework of MMRM, the treatment difference will be tested at each time point.

All secondary endpoints will be evaluated at the 5% level of significance, without adjustment for multiple comparisons.

Details on the analysis of individual secondary endpoints will be provided in the SAP.

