3. ENDPOINTS AND BASELINE VARIABLES: DEFINITIONS AND CONVENTIONS

3.1. Primary and Secondary Endpoints

Section 2.1 lists the overall study objectives and endpoints. The primary, key secondary and secondary endpoints for the purpose of overall study reporting and publications are also detailed in Table 3. Table 4 lists the primary and secondary endpoints of the study organized by known regional requirements.

Table 3. Primary and Secondary Endpoints for Overall Study Reporting and Publications

Alpha (α)	0.05 (2-sided significance level)
Primary Endpoint	Response based on an absolute SALT Score ≤ 20 at Week 24.
Key Secondary Endpoint	Response based on an absolute SALT Score ≤ 10 at Week 24.
Secondary Endpoints	
 Response based on an absolute SALT Score ≤ 20 at Week 24 will be used to characterize the exposure response.

Table 3. Primary and Secondary Endpoints for Overall Study Reporting and Publications

	
 Response based on an absolute SALT score ≤ 20 at Weeks 4, 8, 12, 18, 28, 34, 40, and 48. NOTE: Response at Weeks 4, 8, 12, and 18 will be analyzed controlling for Type I error. Response based on an absolute SALT score of ≤ 10 at Weeks 4, 8, 12, 18, 28, 34, 40, and 48. Response based on a 75% improvement in SALT score from baseline (SALT75) at Weeks 4, 8, 12, 18, 24, 28, 34, 40, and 48. Change from baseline in SALT scores at Weeks 4, 8, 12, 18, 24, 28, 34, 40, and 48. Response based on at least a 2-grade improvement or a score of 3 in EBA at Weeks 4, 8, 12, 18, 24, 28, 34, 40, and 48. Response based on at least a 2-grade improvement or a score of 3 in ELA at Weeks 4, 8, 12, 18, 24, 28, 34, 40, and 48. PGI-C response defined as a PGI-C score of “moderately improved” or “greatly improved” at Weeks 4, 8, 12, 18, 24, 34, 40, and 48. Change from baseline in AAPPO scales at Weeks 4, 8, 12, 18, 24, 34, 40, and 48.
--	--

Table 4. Primary and Secondary Endpoints Organized by Known Regional Regulatory Requirements

	For the FDA/PMDA	For the EMA and competent authorities in the VHP countries
Alpha (α) CCI	0.00125 (2-sided significance level)	0.01 (2-sided significance level)
Primary Endpoint	Response based on an absolute SALT Score ≤ 20 at Week 24.	Response based on an absolute SALT Score ≤ 10 at Week 24.
Key Secondary Endpoint	Not applicable	PGI-C response defined as a PGI-C score of “moderately improved” or “greatly improved” at Week 24.

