- Hypothesis 3 (H3) is to test whether the 200 mg QD/30 mg QD dose regimen is superior to placebo for the primary endpoint;

- Hypothesis 4 (H4) is to test whether the 30 mg QD dose regimen is superior to placebo for the primary endpoint;
- Hypothesis 1p (H1p) is to test whether the 200 mg QD/50 mg QD dose regimen is superior to placebo for the key secondary endpoint;
- Hypothesis 2p (H2p) is to test whether the 50 mg QD dose regimen is superior to placebo for the key secondary endpoint;
- Hypothesis 3p (H3p) is to test whether the 200 mg QD/30 mg QD dose regimen is superior to placebo for the key secondary endpoint;
- Hypothesis 4p (H4p) is to test whether the 30 mg QD dose regimen is superior to placebo for the key secondary endpoint.

The family-wise Type I error will be strongly controlled using a gatekeeping approach as described in the following order and shown in [Figure 2](#). The 10 mg group comparison to placebo is not included in the Type I error controlled procedure, as this group is only included to support the estimation of the exposure response.

[figure not shown]
- The primary endpoint for 200 mg QD/50 mg QD dose regimen (H1) will be tested at α significance level first. If significant, then the primary endpoint for 50 mg QD dose regimen and the 200 mg QD/30 mg QD dose regimen (H2 and H3) and the key secondary endpoint for 200 mg QD/50 mg QD dose regimen (H1p) will be tested simultaneously. If both the 50 mg QD dose regimen and the 200 mg QD/30 mg QD dose regimen are significant, then the 30 mg QD dose regimen will be tested.
- For the primary endpoint, if both the 50 mg QD dose regimen and the 200 mg QD/30 mg QD dose regimen are significant at $\alpha/4$ level, or if one of the dose regimens (50 mg QD dose regimen or 200 mg QD/30 mg QD dose regimen) is significant at $\alpha/4$ level and the other is significant at $\alpha/2$ level, both dose regimens will be declared as significant. In this case, the 30 mg QD dose regimen will be tested at $\alpha/2$ level. If only one of the regimens (50 mg QD dose regimen or 200 mg QD/30 mg QD dose regimen) is significant at $\alpha/4$ level and the other is not significant at $\alpha/2$ level, only the one significant at $\alpha/4$ level will be declared as statistically significant. In this case, the testing for the 30 mg QD dose regimen will not proceed.

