- For the key secondary endpoint, the 200 mg QD/50 mg QD dose regimen will be tested at $\alpha/2$ level first. If significant, then the 50 mg QD dose regimen and the 200 mg QD/30 mg QD dose regimen will be tested simultaneously. If both the 50 mg QD dose regimen and the 200 mg QD/30 mg QD dose regimen are significant at $\alpha/4$ level, or if one of the dose regimens (50 mg QD dose regimen or 200 mg QD/30 mg QD dose regimen) is significant at $\alpha/4$ level and the other is significant at $\alpha/2$ level, both dose regimens will be declared as significant. In this case, the 30 mg QD dose regimen will be tested at $\alpha/2$ level. If only one of the

regimens (50 mg QD dose regimen or 200 mg QD/30 mg QD dose regimen) is significant at $\alpha/4$ level and the other is not significant at $\alpha/2$ level, only the one significant at $\alpha/4$ level will be declared as statistically significant. In this case, the resting for the 30 mg QD dose regimen will not proceed.

- If the primary endpoint for the 200 mg QD/50 mg QD dose regimen is significant at α level, and all the remaining hypotheses for the primary endpoint and key secondary endpoint are significant at the overall $\alpha/2$ level, then all 8 hypotheses will be declared as statistically significant.
- If the primary endpoint for all 4 hypotheses or the primary endpoint for H1 is significant and the key secondary endpoint is significant in all 4 hypotheses, then the $\alpha/2$ level will be passed to the hypothesis testing for the other hypotheses. In this case, the other hypotheses can be tested at the α level instead of the $\alpha/2$ level following the same procedures for claiming statistical significance outlined in the bullets above with the exception of the increased α .

Figure 2. Schematic and Graphical Presentation for Multiple Testing Procedure Incorporating a Key Secondary Endpoint

The numbers on each edge indicate the transition rule for the weights on α allocation once a hypothesis is rejected.

The following approach will be used to control the Type I error for SALT ≤ 20 at earlier time points:

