- For a given dose, if the primary endpoint of SALT ≤ 20 is declared to be statistically significant based on the testing procedure for the primary endpoint, in order to establish the onset of efficacy as measured by SALT ≤ 20 at the earliest time point, a step-down approach with SALT ≤ 20 from Week 24 to earlier time points (order of testing: Weeks 24, 18, 12, 8, and 4) will be used for each time point. Although this testing scheme does not protect the Type I error for the family of all possible comparisons, it will provide Type I error protection for testing the family of SALT ≤ 20 time points within the same dose group.

5.1.2. For the FDA/PMDA (Testing Procedure for Multiple Comparisons with no Key Secondary Endpoints)

[figure not shown]
For the FDA/PMDA, the SALT ≤ 20 response at Week 24 is the primary endpoint and no secondary endpoints will be analyzed as key secondary. The hypotheses to be tested at $\alpha = 0.00125$ are that each of the active treatment groups is superior to placebo as measured by the proportion of subjects achieving the primary endpoint. There are a total of 4 hypotheses to be tested.

- Hypothesis 1 (H1) is to test whether the 200 mg QD/50 mg QD dose regimen is superior to placebo for the primary endpoint;
- Hypothesis 2 (H2) is to test whether the 50 mg QD/50 mg QD dose regimen is superior to placebo for the primary endpoint;
- Hypothesis 3 (H3) is to test whether the 200 mg QD/30 mg QD dose regimen is superior to placebo for the primary endpoint;
- Hypothesis 4 (H4) is to test whether the 30 mg QD/30 mg QD dose regimen is superior to placebo for the primary endpoint.

The family-wise Type I error will be strongly controlled using a gate-keeping approach to test these hypotheses in 3 groups as shown in Figure 3. The first group includes H1; the second group includes H2 and H3; and the third group includes H4. The statistical significance of the first hypothesis (H1) will allow simultaneous testing of H2 and H3 using Holm's method. Statistical significance for both H2 and H3 will enable testing the statistical significance for the fourth hypothesis (H4). The 10 mg group comparison to placebo is not included in the Type I error controlled procedure, as this group is only included to support the estimation of the exposure response.

Figure 3 shows a schematic of the procedure for testing each of the active treatment groups versus the placebo group for the primary endpoint.

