Figure 3. Schematic and Graphical Presentation for Multiple Testing Procedure

The numbers on each arrow indicate the transition rule for the weights on α allocation once a hypothesis is rejected.

In the simultaneous testing of H2 and H3, if both the 50 mg QD/50 mg QD and 200 mg QD/30 mg QD regimens are not significant at $\alpha/2$ level, the test for statistical significance is stopped. If one of the hypotheses for 50 mg QD/50 mg QD and 200 mg QD/30 mg QD regimens is significant at $\alpha/2$ level and the other hypothesis is significant at α level, this family hypothesis is significant. If one of the hypotheses for 50 mg QD/50 mg QD and 200 mg QD/30 mg QD is significant at $\alpha/2$ level and the other hypothesis is not significant at α level, only the hypothesis significant at $\alpha/2$ level will be declared as statistically significant. In this case, the testing for statistical significance for H4 will not proceed.

The following approach will be used to control the Type I error for testing SALT ≤ 10 at Week 24:

- For a given dose, if SALT ≤ 20 at Week 24 is declared to be statistically significant based on the testing procedure for the primary endpoint(s), then SALT ≤ 10 at Week 24 will be tested at the same significance level as the SALT ≤ 20 at Week 24 was tested. Though this testing scheme does not protect the Type I error for the family of all possible comparisons, it will provide Type I error protection for testing the endpoints within the same dose group.

The following approach will be used to control the Type I error for testing SALT ≤ 20 at earlier time points:

- For a given dose, if the primary endpoint of SALT ≤ 20 at Week 24 is declared to be statistically significant based on the testing procedure for the primary endpoint, in order to establish the onset of efficacy as measured by SALT ≤ 20 at the earliest time point, a step-down approach with SALT ≤ 20 from Week 24 to earlier time points (order of testing: Weeks 24, 18, 12, 8, and 4) will be used for each time point. Though this testing scheme does not protect the Type I error for the family of all possible comparisons, it will provide Type I error protection for testing the family of SALT ≤ 20 time points within the same dose group.

5.1.3. For the EMA and Competent Authorities in the VHP Countries (Testing Procedure for Multiple Comparisons Incorporating the PGI-C Response as a Key Secondary Endpoint)

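### Does the onset step-down through Weeks 18, 12, 8 and 4 need a written significance level before it can be used?

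*SAP*

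**What the plan says.** SAP 5.1.1 (overall study), 5.1.2 (FDA/PMDA) and 5.1.3 (EMA and VHP authorities) share one device. If a dose's Week 24 primary endpoint is declared significant, earlier visits are tested in turn: "order of testing: Weeks 24, 18, 12, 8, and 4) will be used for each time point". The overall and FDA/PMDA plans step down on SALT ≤20, the EMA plan on SALT ≤10. Protocol 9.2.1.1 to 9.2.1.3 say the same.

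The claim attached is limited. The SAP states that the scheme does not protect the family of all possible comparisons, then says "it will provide Type I error protection for testing the family of SALT" time points within the same dose group (shown here from the SALT ≤20 plans). SAP Tables 3 and 4 list the visits as controlled: "NOTE: Response at Weeks 4, 8, 12, and 18 will be analyzed controlling for Type I error".

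The Week 24 levels come from the gatekeeping bullets. In 5.1.1, 200/50 mg is tested at α. The 50 mg and 200/30 mg pair is tested at α/4, with the second member allowed α/2. If the pair succeeds, "both dose regimens will be declared as significant. In this case, the 30 mg QD dose regimen will be tested at" α/2. Once one endpoint is significant in all four doses, α/2 is passed on: "In this case, the other hypotheses can be tested at the α level instead of the" α/2 level. Section 5.1.3 repeats this at α = 0.01. Section 5.1.2 uses Holm's method at α = 0.00125 with no recycling between endpoints.

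For the other SALT threshold at Week 24, 5.1.2 does tie the level to the gate: it "will be tested at the same significance level as the SALT" ≤20 test. Section 5.1.3 has a matching sentence. The step-down bullets have none.

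**The concern.** A fixed sequence needs an order, a gate and a level, and the third is not written. The gate alone does not supply it for every dose. A Week 24 p-value of 0.001 for 50 mg is below 0.0125, 0.025 and 0.05, so knowing that Week 24 was significant does not by itself say which level goes down to Week 18.

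The step-down exists to name the earliest visit with an effect. Two analysts could name different onset visits from the same data, or a level could be settled after the p-values are known. The protocol's statistical summary adds a further candidate: "All secondary endpoints will be evaluated at the 5% level of significance, without adjustments for multiple comparisons".

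**Working it through.** **1. Candidate levels, from SAP 5.1.1 to 5.1.3.** The pair is 50 mg and 200/30 mg, ranked by p-value.

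| Plan | 200/50 mg | Pair, smaller p / larger p | 30 mg | After recycling: pair; 30 mg |
|---|---|---|---|---|
| Overall, α = 0.05 | 0.05 | 0.0125 / 0.025 | 0.025 | 0.025 / 0.05; 0.05 |
| FDA/PMDA, α = 0.00125 | 0.00125 | 0.000625 / 0.00125 | 0.00125 | none |
| EMA, α = 0.01 | 0.01 | 0.0025 / 0.005 | 0.005 | 0.005 / 0.01; 0.01 |

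The FDA/PMDA entry for 30 mg assumes the full α passes on once both pair members are rejected. Figures 2 and 3 are not shown in the text, so the levels come from the bullets.

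**2. The plan's own figure.** SAP 2.2.1 states more than 90% power for 29% v 5% with 120 per group at two-sided 0.05. Pooled-variance approximation: mean rate 0.17; null SE = √(2 × 0.17 × 0.83/120) = 0.0485; alternative SE = √((0.29 × 0.71 + 0.05 × 0.95)/120) = 0.0460. Power = Φ((0.24 − 1.96 × 0.0485)/0.0460) = 99.9%. At 0.0125 it is 99.5%, and at 0.00125 it is 96.5%. Week 24 is insensitive to the level; only the earlier visits can be affected.

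**3. Does the promised protection depend on the missing level?** Within one dose, take the first visit in the order at which the null is true. Any false rejection requires that visit to be rejected, which has probability at most the level used there. Every candidate is at most α, so within-dose error is at most α under each of them.

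**4. What a single visit can do.** Miettinen–Nurminen score test of zero difference, 120 v 120: z = (x₁ − x₀)/120 ÷ √(p(1 − p)(2/120)(240/239)), with p = (x₁ + x₀)/240.

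- 9 v 2 responders: p = 11/240, z = 0.0583/0.0271 = 2.16, two-sided p-value 0.031. Significant at 0.05 but not at 0.025.
- 10 v 2 responders: p = 12/240, z = 0.0667/0.0282 = 2.36, p-value 0.018. Significant at 0.025 but not at 0.0125.

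Exact enumeration with assumed true rates of 2% v 8% gives significance in 35.2% of trials at 0.0125, 45.7% at 0.025 and 58.2% at 0.05. The α/4 v α/2 choice therefore decides 45.7 − 35.2 = 10.5% of trials at such a visit.

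**5. Effect on the reported onset visit.** The documents give no earlier-visit rates. The assumptions are Week 24 rates of 22–29% active and 2% or 5% placebo; linear, late or early build-up; visits monotone within subject or independent; and a Week 24 result that passes at the lower level. The share of trials in which one dose's onset visit differs is:

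- overall, 0.0125 v 0.025: 18–37%;
- FDA/PMDA, 0.000625 v 0.00125: 10–23%;
- overall, 0.0125 v 0.05: 35–59%.

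The last line is not a fair measure. For the pair, 0.05 arises only through recycling, and these are trials in which the dose had already been rejected at 0.0125.

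**6. Error across four doses, for context.** Take every gate passed, the visit null in all doses, null rates of 2–5% and overall α = 0.05. Counting only drug-favouring rejections, which alone can support an onset claim, the rate is 3.1–3.6% at the starting levels (α, α/4, α/4, α/2) and 5.3–6.1% at the recycled levels (α, α/2, α, α). Counting both directions gives 6.2–7.6% and 11.9–12.8%. The SAP disclaims this family, so none of these figures breaches the plan.

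**The case for a change.** The strongest argument is that the sponsor wrote the level for the neighbouring Week 24 threshold and left it out here, while listing the earlier visits as controlled. Carrying the gate level down settles 200/50 mg, but the pair still has two levels in each plan, and the overall and EMA plans recycle. Step 5 shows the reported onset can move.

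The omission stands, and so does a limited ambiguity for the pair. Much of the rest closes on ordinary reading. Week 24 heads the listed sequence. Section 5.1.2 names Holm's method, which assigns levels by p-value rank, so a p-value below several thresholds still has one assigned level; the pair rule in 5.1.1 and 5.1.3 has the same form at half the level. Recycled α goes to the other hypotheses, naturally those still open, and a dose already rejected does not need it. The rule for the other Week 24 threshold refers to the level at which that test was carried out, which is the same convention.

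The unrestricted 5% sentence in the protocol summary is a drafting slip. Protocol 9.2.3 confines that rule with "For all regions, analyses of secondary endpoints that are not" α controlled, which excludes these visits.

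**Conclusion.** The level is not written, but no change to the plan follows. This is missing detail that an analyst fills by convention: the level at which that dose's Week 24 primary hypothesis was rejected, Holm-ranked for the pair and not raised by later recycling. No stated rule gives a wrong result. Within-dose protection holds at every candidate level, protection across doses is openly disclaimed, and primary and key secondary conclusions do not depend on the choice.

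The residual effect is a possible shift in a secondary onset description for 50 mg or 200/30 mg: 18–37% of trials for α/4 v α/2 in the overall study, and 10–23% for α/2 v α under FDA/PMDA. These ranges rest on the assumed earlier-visit rates in step 5, and some of the scenarios treat visits as independent, which is unlikely for regrowth in the same subjects. For 30 mg, the only question is whether recycled α counts. The EMA plan has the same structure, but its earlier visits are analysed with the GLMM, so the Miettinen–Nurminen figures do not transfer directly.

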5.2. General Methods

In general, number and percent will be presented for binary variables. Number, mean, standard deviation (or standard error of the mean), median, minimum, and maximum will be presented for continuous variables.

For analyses up to Week 24, in the comparison to placebo, the data from both placebo groups (F and G) will be pooled to form a combined placebo group. For analyses up to Week 48, data will be summarized by 7 treatment sequences ([Figure 1](#)) without combining two placebo groups.

5.2.1. Binary Endpoints

Planned analysis for the overall study, for the FDA/PMDA and for the EMA and competent authorities in the VHP countries are summarized in Table 5.

Table 5. Statistical Methods of Planned Analysis for Primary and Key Secondary Endpoints for the Study and for each Regulatory Region

Study or Region	Endpoint/designation	Analysis #	Analysis Designation	Statistical Method	Missing due to COVID-19	Missing due to other reasons
Overall Study	SALT \leq 20 at Week 24/primary	Analysis 1	Primary	MN	Exclude	non-responders
		Analysis 2	Supplementary	GLMM	MAR	MAR
		Analysis 2a	Supplementary	GLMM/TP	MNAR	MNAR
		Analysis 3	Supplementary	MN	non-responders	non-responders
	SALT \leq 10 at Week 24/key secondary	Analysis 1	Key Secondary	MN	exclude	non-responders
		Analysis 3	Supplementary	MN	non-responders	non-responders
FDA/PMDA	SALT \leq 20 at Week 24/primary	Analysis 1	Primary	MN	exclude	non-responders
		Analysis 2	Supplementary	GLMM	MAR	MAR
		Analysis 2a	Supplementary	GLMM/TP	MNAR	MNAR
		Analysis 3	Supplementary	MN	non-responders	non-responders
EMA and competent authorities in VHP countries	SALT \leq 10 at Week 24/primary	Analysis 4	Primary	GLMM	MAR	non-responders
		Analysis 4a	Supplementary	GLMM/TP	MNAR	non-responders
		Analysis 1	Supplementary	MN	exclude	non-responders
		Analysis 3	Supplementary	MN	non-responders	non-responders
	PGI-C Response at Week 24/key secondary	Analysis 4	Key Secondary	GLMM	MAR	non-responders

Abbreviations: GLMM = Generalized linear mixed model; MN = Miettinen and Nurminen; MAR = Missing at random; MNAR = Missing not at random; TP = Tipping point

5.2.1.1. Miettinen and Nurminen – Analysis 1 and Analysis 3

The Miettinen and Nurminen (MN) method will be used to calculate 95% confidence intervals (CI) and p-values for the difference in the proportion of responders between each active treatment group and placebo. Subjects with missing SALT score at Week 24 due to COVID-19 related reasons will be excluded from the analysis at that time point, whereas subjects with missing SALT scores due to other reasons will be counted as non-responders at that time point (Analysis 1).

As a supplementary analysis to assess the impact of COVID-19-related missing data on the results of the primary analysis, a similar analysis will be conducted with all missing data considered as non-responders regardless of the reason for missingness (Analysis 3).

